We selected villages for participation in this study based on our prior work and established relationships, and villages that had sufficient numbers of pregnant women each year. In 2011, over a 9 month period there were 16 villages with at least 15 women seen for a 1st prenatal visit (Table 1). This estimate was conservative because it does not reflect all women with a positive pregnancy test. Sixteen villages were stratified based on village size (<600 and >600) and randomly assigned to receive the intervention (8 villages) or control condition (8 villages).

Table 1. Village count of pregnant women seen for a 1st visit Jan-Sept 2011 (excludes Bethel)

# pregnant women	# villages
1-9	20
10-14	9
15-19	7
20-25	8
26-30	1
31-35	0
36-44	3

The research coordinator and study staff met with the respective village tribal councils and village health aide staff of all 16 villages to enlist their participation. We have successfully used this approach in our previous group-randomized trial in this region.

Recruitment of pregnant women within each village will occur over an 25-month period. We attempted to enroll at least 22 pregnant women from each of the 16 villages, accounting for an estimated rate of attrition of 10% based on prior studies due to miscarriage, abortion or fetal demise, to achieve a final sample of at least 320 women eligible for follow-up. Recruitment delays were encountered and thus NIH funding was extended from 5 to 6 years (see Table 4). We will request a no cost extension from NIH for a 7th project year which will enable us to complete analyses and dissemination as remaining funds permit.

Recruitment:

A study logo that consists of a baby in womb and the text “*Healthy Pregnancies*” was created by Northwest Strategies. The logo was placed on all recruitment materials, and will be used on any communications from the research coordinator or study team members.

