who quit tobacco use during pregnancy, the relapse rate was 63% at 6 weeks postpartum. Of the 432 women reporting no tobacco use in the three months before pregnancy, 75% reported tobacco use during the prenatal period, and 70% at 6 weeks postpartum. Alaska PRAMS data indicate similar cessation rates during pregnancy (20%) and rates of relapse postpartum (57%) in the southwest region. During the time periods these estimates were obtained, women received the same standard of care as in the proposed study. Therefore, we do not expect our usual care condition to impact tobacco use beyond the natural history of tobacco use in pregnancy. The Clinical Practice Guideline meta-analysis found that behavioral/psychosocial interventions for pregnant smokers were associated with an abstinence rate of 13% in late pregnancy vs. 7% for control conditions (OR= 1.8, 95% CI 1.5-2.3). We do not have guidance from the literature on the possible impact of interventions for baseline non-tobacco users but would expect greater impact in this group compared to those already using tobacco. Accordingly, we estimate the rate of tobacco use at 6 months postpartum to be 70% in our control villages and 55% in the intervention villages (estimated odds ratio 1.91) and in late pregnancy to be 80% vs. 65% with an odds ratio of 2.15. A difference of 15% would be of clinical significance in terms of the potential to impact the current standard of care at the YKDRH.

Estimates of intra-class correlations (ICC) within communities are quite modest, e.g., ranging from 0.002 to 0.012 for a variety of survey variables included in the Minnesota Heart Health Program. For the proportion currently smoking the estimated ICC was 0.00272. Other literature indicates that in community based trials using group-randomized designs (e.g., NCI Working Well Trial) the ICC ranged from 0.01-0.03 for the four outcome variables at baseline. Lumley et al. reviewed 9 cluster randomized trials of prenatal cessation interventions but most did not report the ICC and/or account for the clustering effect in the analysis. Table 3 (below) provides power estimates for the estimated outcomes with 16 villages total, average village participant size of 20 (total sample size = 320), and with varying ICC estimates. With an ICC of 0.01 we will have >80% power to detect the hypothesized differences between conditions at 6 months postpartum.

Table 3. Power estimates for 1-sided alpha=0.05 test

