ICC	Hypothesized difference in tobacco use rates	
	Late Pregnancy 65 vs. 80%	6 Months Postpartum 55 vs. 70%
0	91	87
0.001	91	86
.01	86	81
.02	82	76
.03	77	71

Data Analysis Plan:

Analyses will be performed by [name], M.S. who has extensive experience in analysis of randomized clinical

trials, with consultation from [name]. Recruitment data will be summarized, including the total number of potential participants screened from each village, the number excluded for each of the specific inclusion/exclusion criteria, and the number of eligible women who agree to participate. To assess reach of the program in each village, we will calculate the proportion of subjects enrolled to total eligible subjects. We will compare the recruitment rates between control and intervention villages using the chi-square test. Potential village effects on recruitment rate will be explored.

Baseline demographics will be summarized and compared between intervention and control villages using the chi-square test for categorical variables and the two-sample t-test/rank sum test for continuous variables. The biochemically confirmed 7-day point prevalence tobacco use rate at 6 months postpartum will be summarized for each condition (point estimate and 95% CI) among participants eligible for follow-up (i.e., excluding women experiencing a miscarriage, abortion or fetal demise) and compared between conditions using generalized estimating equations (GEE) with a logit link function to account for clustering of outcomes within village (ICC) (**Aim 1**). We will utilize an intent-to-treat approach, with participants eligible but lost to follow-

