up or who do not provide biochemical confirmation classified as using tobacco. The analysis will be supplemented with multiple imputation methods to classify lost to follow-up as tobacco users or non-users. GEE will also be used to examine condition differences on the point prevalence tobacco use rates at 12 weeks/week 36 gestation, and at 8 weeks postpartum. Because only 14 df are available for the test of the intervention we will employ a small sample correction to the standard GEE. For these analyses, the stratification factor (village size) will be adjusted for in the analysis. Based on the biochemically confirmed tobacco use status at baseline, in an exploratory fashion we will examine potential treatment effects separately among baseline non-tobacco users and tobacco users respectively using GEE. Within intervention villages only, exposure dose will be tested as a predictor of tobacco use at 36 weeks gestation and 6 months postpartum using GEE. A similar analysis will be performed using the intervention implementation index to examine potential dose response effects. Assuming an ICC of 0.01 and an effective sample size of 135 subjects in the intervention arm after correction for the ICC, there will be 80% power to detect an effect size of at least 0.5 standard deviation units when examining the association of intervention exposure (i.e., continuous measure) and abstinence rates. Potential village differences on intervention exposure or implementation will be summarized graphically and compared using GEE. The percentage of enrolled participants who complete 6- month follow-up postpartum (retention) will be compared between intervention and control villages using GEE.

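### The stated 14 df for the intervention test leaves out the village-size stratum that the same analyses adjust for; the between-village count is 13, and the effect is conditional and very small

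*Combined protocol and SAP*

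**What the plan says.** The Randomization section gives the design: "Sixteen villages were stratified based on village size (<600 and >600" and then "randomly assigned to receive the intervention (8 villages) or control condition (8 villages". There are therefore 16 clusters, two arms and a stratifier with two levels.

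Under Statistical Considerations, Phase II, the Data Analysis Plan says that the primary outcome, biochemically confirmed tobacco use at 6 months postpartum, will be "compared between conditions using generalized estimating equations (GEE) with a logit link function to account for clustering of outcomes within village (ICC". The same method is then applied to tobacco use at 12 weeks/week 36 gestation and at 8 weeks postpartum. Two sentences follow directly. The first reads "Because only 14 df are available for the test of the intervention we will employ a small sample correction to the standard GEE". The second reads "For these analyses, the stratification factor (village size) will be adjusted for in the analysis".

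The plan does not say which small-sample correction will be used. It also names no t or F reference distribution for the test.

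**The concern.** The df figure and the model are described in consecutive sentences, and they do not agree. A village-level covariate is constant within a village, so it is estimated from between-village information, as the arm effect is. A count of 14 fits a model with an intercept and an arm term only. The planned model also carries the stratum.

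The df matters because many small-sample procedures for clustered data refer the test statistic to a t or F distribution with a between-cluster df. If 14 is carried into such a procedure, the critical value is slightly too small, so the error is in the anti-conservative direction. The comparisons affected are those that precede the adjustment sentence: 6 months postpartum, 12 weeks/week 36 gestation and 8 weeks postpartum.

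**Working it through.** **Inputs**
- Villages: 16, allocated 8 to each arm (Randomization).
- Stratifier: village size, two levels (Randomization), adjusted for in the analysis (Data Analysis Plan).
- Stated df: 14 (Data Analysis Plan).
- Power inputs: 320 women, 20 per village; 55% against 70% at 6 months postpartum; one-sided alpha 0.05; 81% power at an ICC of 0.01 (Power Statement and Table 3).

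**Step 1. Reproduce the stated figure.** Villages less arms: 16 - 2 = 14. This matches the plan and is the count without the stratum.

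**Step 2. Count for the planned model.** The village-level parameters are the intercept, arm and one term for the two-level stratum: 16 - 3 = 13.

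**Step 3. Effect if the test is referred to t.**

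| 5% test | Critical value, 14 df | Critical value, 13 df | Ratio | Actual error if the 14-df value is used and 13 df applies |
|---|---|---|---|---|
| Two-sided | 2.1448 | 2.1604 | 1.0073 | 2 × P(t13 > 2.1448) = 0.0514 |
| One-sided | 1.7613 | 1.7709 | 1.0055 | P(t13 > 1.7613) = 0.0508 |

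A 95% interval for the condition comparison would be about 0.7% too narrow.

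**Step 4. Does Table 3 depend on the 14 df?** At an ICC of 0.01 the design effect is 1 + 19 × 0.01 = 1.19, so the effective number per arm is 160 / 1.19 = 134.5. A one-sided normal-approximation test of 55% against 70% then has 81.8% power; the table states 81%. The same formula reproduces all ten cells of Table 3 to within about one point.

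With a noncentral t and unpooled standard error, SE = √[(0.55 × 0.45 + 0.70 × 0.30) / 134.5] = 0.0583 and the noncentrality is 0.15 / 0.0583 = 2.57. Power is then 78.8% with 14 df and 78.5% with 13 df. The table matches the normal calculation, so it does not use the 14 df. Moving from 14 to 13 would change a t-based power figure by 0.3 points.

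**The case against.** The strongest reply is that 14 is never put to work. It appears once, as the reason for applying a correction, and 13 would be an equally good reason. A reader might infer that the plan fixes a reference distribution for the primary test and that this distribution is too narrow. The documents do not support that. They state no reference distribution, and some small-sample GEE corrections adjust the variance or estimate their own df, in which case the 14 need not enter the test. The only 95% interval that the plan mentions for this outcome is for the rate within each condition, so an interval for the comparison is itself an assumption. This part of the reply stands, and it makes the figures in Step 3 conditional.

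A reader might also infer that every condition comparison in the paragraph is affected. That goes too far. The adjustment sentence covers the analyses before it. The baseline-user subgroup, dose and retention analyses come later, and no df or adjustment is stated for them.

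It can also be said that 13 may not be the effective df. Enrolment ran from 2 to 42 women per village, and such imbalance could lower the effective df by more than the stratum term does. The documents do not give each village's count, so this was not computed. It is a reason not to impose 13 on a correction that estimates its own df.

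None of this reconciles the two sentences. The plan describes 14 as the df available for the intervention test, and that count does not fit the model in the next sentence. Nothing elsewhere in the document resolves it.

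**Conclusion.** The point holds as a mismatch between the stated df and the planned model: 14 should be 13 for the condition comparisons at 6 months postpartum, 12 weeks/week 36 gestation and 8 weeks postpartum. This rests on two assumptions: the conventional between-village count is used, with village size entering as one term, and the adjustment sentence includes the primary 6-month comparison, which is its natural reading.

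The effect is very small and arises only if the test is referred to t with 14 df: about 5.14% error two-sided or 5.08% one-sided instead of 5%, and intervals about 0.7% too narrow. No power or sample-size figure changes. The documents do not show that the primary test, as it will be run, is miscalibrated.

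The choice of correction matters more than 14 against 13. Referring the statistic to the normal distribution when 13 or 14 df apply would give a two-sided error of about 7.2% or 7.0%.

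**What to change.** In the Phase II Data Analysis Plan, replace 14 df with 13 df (16 villages less intercept, arm and village-size stratum), and limit the statement to the condition comparisons at 6 months postpartum, 12 weeks/week 36 gestation and 8 weeks postpartum. Add that 13 is used where the chosen small-sample GEE correction takes a t or F reference with a between-cluster df, and that a correction which estimates its own df keeps its own value. Naming the correction in the same sentence would make clear which case applies.

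The cost is a small text edit and, where the between-cluster df is used, intervals about 0.7% wider. The design, the sample size and Table 3 stay as they are.

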In Phase II, we will conduct an evaluation of the intervention applying a group-randomized design with village as the unit of assignment. Sixteen villages were selected and randomly assigned to receive the intervention (8 villages) or control condition (8 villages) with ≥ 22 pregnant women recruited per village.

Subject population:

Sample size calculation. We estimate recruiting ≥ 22 pregnant women per village (N=352). Accounting for an estimated attrition rate of 10% due to miscarriage, abortion or fetal demise, we plan to achieve a final sample of at least 320 women eligible for follow-up. All pregnant women (tobacco users and non-users) will be eligible for enrollment.

Actual accrual. We met our targeted sample size of 352 women enrolled. Encouragingly, overall participation from control villages (n=164) was similar to overall participation from intervention villages (n=188). Although we estimated 22 or more women enrolled in each village, this was not feasible. Study villages were more or less interested in participating, with a range of 2 to 42 women enrolled in the 16 study villages.

Inclusion Criteria:

Participants consist of 352 Alaska Native pregnant adults age 18 and older. To be eligible for the study, Alaska Native pregnant women participants must:

- Be 18 years of age or older
- Provide written informed consent
- Currently 36 weeks or less gestation
- Access to a working telephone

Exclusion Criteria:

Individuals will be considered ineligible to participate in the study if they are:

- Not Alaska Native
- Under the age of 18
- Currently not pregnant or ≥ 37 weeks gestation
- No access to a working telephone
- Refuse to provide written informed consent

Will a Certificate of Confidentiality be obtained? If yes, provide an explanation.

No, a Certificate of Confidentiality will not be obtained.

Study Design

Methods: *Describe, in detail, the research activities that will be conducted under this protocol:*

Phase IA. Social Marketing Campaign Development

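### The plan estimates the intervention effect separately in baseline users and non-users, but gives no estimate of how far the two effects differ

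*Combined protocol and SAP*

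**What the plan says.** The Data Analysis Plan for Phase II (Statistical Considerations) classifies women by biochemically confirmed tobacco use at baseline and states: "in an exploratory fashion we will examine potential treatment effects separately among baseline non-tobacco users and tobacco users respectively using GEE". Nothing else in that section concerns a comparison of the two subgroups. It contains no condition-by-baseline-status interaction, no interval for a difference in effects, and no rule for reading the two results together. No power is given for either subgroup.

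The Power Statement does say which way the authors expect the effects to differ. Of baseline non-users it says that they "would expect greater impact in this group compared to those already using tobacco". The intervention has content aimed at cessation and content aimed at preventing initiation (Phase IB; Individual components), and the Recruitment section explains that users and non-users were both eligible so that the trial could address both.

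**The concern.** Because the plan expects a larger effect in non-users and has separate prevention and cessation content, the two subgroup results will naturally be read side by side. The Dissemination Plan takes the results to the tribal health board, local providers and statewide partners. If one subgroup effect is significant and the other is not, it is easy to read the programme as working for prevention but not cessation, or the reverse. That pattern is not evidence that the effects differ, because each subgroup has limited power and chance alone often produces it. As written, the plan yields no figure that would tell a reader how much of an apparent gap is noise.

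**Working it through.** **Inputs from the documents.** The Power Statement gives the rates: "we estimate the rate of tobacco use at 6 months postpartum to be 70% in our control villages and 55% in the intervention villages", with "estimated odds ratio 1.91". Sixteen villages (8 per arm) average 20 women each, so 320 in total and 160 per arm. The plan's power basis is headed "Table 3. Power estimates for 1-sided alpha=0.05 test".

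**Reproducing the plan's own figure.** The claim is: "With an ICC of 0.01 we will have >80% power to detect the hypothesized differences between conditions at 6 months postpartum"; Table 3 gives 81%. The design effect is 1 + (20 − 1) × 0.01 = 1.19, so the effective size is 160/1.19 = 134.5 per arm. In a one-sided pooled z test the critical difference is 1.645 × √(2 × 0.625 × 0.375/134.5) = 0.0971. The standard error under the alternative is √((0.70 × 0.30 + 0.55 × 0.45)/134.5) = 0.0583. Power is Φ((0.15 − 0.0971)/0.0583) = 81.8%. All ten cells of Table 3 come back within about 1 point, so the framework matches the plan's.

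**Inputs that must be assumed.**
- Share of baseline users: 50% to 79%. The Background gives regional figures of 48% before pregnancy and 79% during pregnancy.
- Control use: 70% in both groups. This keeps the plan's overall rate. The only subgroup rates in the Power Statement are 69% and 70% at 6 weeks postpartum, and those are split by pre-pregnancy use, not by baseline status.
- Equal ICC in both groups, equal village sizes, and the 6-month outcome.

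**Subgroup power when the true effect is identical.** The odds ratio is (0.70/0.30)/(0.55/0.45) = 1.909 in both groups. For a subgroup with share f, the effective size per arm is n = 160f/[1 + (20f − 1) × 0.01]. Power is Φ(0.15/√(0.4575/n) − z), with z = 1.645 one-sided or 1.960 two-sided (unpooled variance, 0.21 + 0.2475 = 0.4575). With power Pu in users and Pn in non-users, the chance that exactly one is significant is Pu(1 − Pn) + Pn(1 − Pu).

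Example with f = 0.50: n = 80/1.09 = 73.4 and 0.15/√(0.4575/73.4) = 1.900. Power is Φ(0.255) = 60% one-sided and Φ(−0.060) = 48% two-sided. The one-sided chance that exactly one is significant is 2 × 0.601 × 0.399 = 48%.

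| Baseline users | Effective n per arm: users / non-users | One-sided power: users / non-users | Exactly one significant | Two-sided power: users / non-users | Exactly one significant |
|---|---|---|---|---|---|
| 50% | 73.4 / 73.4 | 60% / 60% | 48% | 48% / 48% | 50% |
| 60% | 86.5 / 59.8 | 66% / 53% | 49% | 54% / 40% | 51% |
| 70% | 99.1 / 45.7 | 71% / 44% | 52% | 60% / 32% | 53% |
| 79% | 110.1 / 32.6 | 75% / 35% | 57% | 64% / 24% | 57% |

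**Checks on this result.**
- The formula treats the subgroups as independent, although they share villages. A simulation with a shared village effect and village-level t tests on 14 degrees of freedom (4,000 runs per setting, 50% to 80% users) gives 46% to 53% one-sided and 45% to 52% two-sided.
- Control rates of 80% in users and 50% in non-users give about 49% to 55%.
- With no effect in either group, the figure is 2 × 0.05 × 0.95 = 9.5%.

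**What an interaction estimate would add.** The variance of each log odds ratio is (1/0.21 + 1/0.2475)/n = 8.80/n. The standard error of the log ratio of odds ratios is therefore √(0.120 + 0.120) = 0.49 at 50% users and √(0.080 + 0.270) = 0.59 at 79%. Under a common effect, a two-sided 5% interaction test signals a difference in 5% of trials by construction (4.6% to 5.5% in the simulation). For 80% power the true ratio of odds ratios would have to be exp(2.80 × 0.49) = 3.9 to exp(2.80 × 0.59) = 5.2.

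**The case against.** The strongest reply is that the plan makes no error of inference. A reader might infer that it will compare subgroup p-values, or will declare that the programme works in one group and not in the other. The documents do not support that: the analysis is labelled exploratory, and no such comparison or claim is stated. Nor is effect modification one of the aims, hypotheses or endpoints. The expectation about non-users is one clause supporting the assumed overall rates. This part of the reply stands.

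A reader might also infer that separate models are the wrong method. They are not wrong for describing each group: in non-users the outcome reflects prevention and in users cessation, and both are worth reporting. A joint model would give nearly the same two estimates. What is missing is one contrast with its interval.

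The size depends on a user share and subgroup control rates that the documents do not give, and the figure of about one half is specific to a common odds ratio of 1.91. That is a fair limit, but the figure moves little across the settings tried, one-sided or two-sided.

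Finally, the interaction has little power. For illustrative odds ratios of 1.4 in users and 2.6 in non-users, it is about 18% to 24%. This is a reason to report the interaction as an estimate, not to leave it out, because the wide interval is what tells readers that the data cannot separate the two effects.

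**Conclusion.** The point holds as a gap in an exploratory analysis. The separate estimates are valid description, but they cannot show whether the effect differs, and the plan supplies nothing that can. If the true odds ratio were 1.91 in both groups, about 48% to 57% of trials would show one significant and one non-significant subgroup. With no effect in either group it would be about 10%. These figures assume ICC 0.01, 320 women, 70% control use in both groups and 50% to 79% baseline users. Actual enrolment of 2 to 42 women per village would probably make subgroup precision worse than computed here.

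The weight is small: the primary comparison, endpoint and sample size are untouched. The documents do not support the stronger conclusion that the trial is set to report a false prevention-versus-cessation split. That would need a step in the later report which the plan does not describe.

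**What to change.** Fit one GEE with condition, biochemically confirmed baseline status, their interaction and the village-size stratum, using the small-sample correction already planned. From that model report the effect in users, the effect in non-users and the ratio of the two odds ratios, each with a 95% confidence interval. Keep the exploratory label. Add that no statement about a differential effect will rest on one subgroup being significant and the other not.

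The cost is a sentence or two in the Data Analysis Plan. It needs no new data and no change to the primary analysis. The downside is imprecision: with a standard error of about 0.5 to 0.6 on the log scale, only a ratio of odds ratios of about 4 to 5 would be detected with 80% power. The text should therefore present the interaction as an estimate, and a non-significant result should not be read as showing equal effects.
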